4.0 Enrollment

The registration process will occur at the Osher Center for Integrative Medicine at Vanderbilt, located at [name], or following telephone screening for the study outside of OCIM. Following study screening, the assessment measures will be completed via computer on-site at OCIM or online through a secure RedCap link. There is no randomization process for this study.

Recruitment

Individuals referred to group hypnosis for pain control at the Osher Center for Integrative Medicine at Vanderbilt (OCIM) will be recruited for potential inclusion in this research study. Referrals to the group hypnosis program at OCIM generally occur in one of three ways: 1) internally within OCIM, 2) through another provider at VUMC, and 3) self-referral. Participants will be made aware of group services available in clinic through word-of-mouth, rotating information posted in waiting rooms regarding group offerings and timetables, and through discussion with providers. In addition, flyers and information regarding this service may be posted at additional outpatient clinics at VUMC per usual practice.

Due to the popularity of this service at OCIM and long waiting list for hypnosis treatment, we do not anticipate having to expand recruitment beyond clinical practice as usual.

Screening Procedures

All patients referred to services at OCIM are seen by a provider first-hand in order to establish an integrative treatment plan as a part of their treatment.

Vanderbilt University Medical Center

Study #: 170652

Revision Date: 2/10/2020

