with higher numbers of participants- may require a little more time than others to ensure each participant has an opportunity to actively participate and discuss.

The group sessions will be initially conducted by the PI and a post-doctoral fellow in Psychology. If the service expands, groups will also be conducted by OCIM/VUMC providers who are competent in practicing clinical hypnosis and/or have undergone a formal two-day training process that prepares clinicians to conduct the intervention in a group setting. Potential providers will be licensed/credentialed/privileged allied health professionals or providers-in-training under supervision from a licensed professional from the following disciplines: Ph.D. licensed Psychologists, advanced Clinical Psychology Doctoral Candidates under the supervision of the PI, Pre-doctoral Clinical Psychology Interns (i.e., who are in their final year of a doctoral degree program and supervised by a licensed Clinical Psychologist) and Psychology Post-doctoral Fellows (who have completed a Ph.D.), Psychiatry Residents, Physical Therapists (PT, DPT), or Nurses (RN). Each provider will participate in a two-day training, which will cover group instruction for self-hypnosis. All study clinicians will also be given regular feedback by the PI ([name]) on their performance. In addition, ongoing consultation will be offered to providers leading self-hypnosis interventions by [name] to ensure that any questions that in real time can be answered.

Each group will be led by two providers allowing for groups to continue as scheduled in the event one of the providers is unable to attend a particular group. Groups will be scheduled to start when at least ten participants are enrolled.

Additional participants will be scheduled for the groups until they reach the maximum size of fifteen. Providers will be expected to follow closely the treatment manuals to ensure all scheduled material is covered, and to ensure the consistency and replicability of treatment.

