Timetable: Once patients are screened and determined to be eligible to participate in the study, they will complete informed consent and an assessment battery online or via computer on-site at OCIM either the same day or returning on a separate day, if requested. They will then be enrolled in the next group series, which we anticipate to occur roughly every two months. With groups occurring 5 times per year with 15 participants, we anticipate a study inclusion rate of 75%. In order to recruit 105 participants with a conservative estimated dropout rate of 45%, including follow-up we anticipate this study will occur over the course of two years.

Revision Date: December 1, 2003

Measures Used

General Information

Demographics: Patients will complete an 12-item brief demographic questionnaire indicating age, gender, race, religious orientation, and household income. Patients will also indicate their diagnoses and information regarding diagnosis/treatment. The questionnaire will take approximately 3 minutes to complete.

Expectancy Questionnaire: Participants will be asked open-ended questions to assess their expectancies and in order to provide qualitative feedback regarding the impact of treatment on their life, health, and functioning. The questions range from a single question to six questions, depending on what timeframe the participant is being assessed.

Pain and Physical Functioning

PainDetect (PD-Q; (44)) is a simple, patient-based, easy to use screening tool to assess the presence of neuropathic and nociceptive pain. It consists of 9 self-report items that assess for the quality, spatial characteristic, and individual pain patterns. It takes roughly 1-2 minutes to complete.

Brief Pain Inventory (severity scale only; (45)) is a 4-item subscale of the Brief Pain Inventory assessing the severity of pain over the past week. Questions inquire into an individual's worst, least, average, and current levels of pain on an 11-point likert scale. It has been validated and is considered the gold standard to utilize in patient-reported outcomes studies (46). It takes <1 minute to complete.

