American Urological Association Symptom Index (AUASI; to be given to participants with Urologic symptoms only (56)) is based on the answers to seven questions concerning urinary symptoms and one question concerning quality of life. Each question concerning urinary symptoms allows the patient to choose one out of six answers indicating increasing severity of the particular symptom. The answers are assigned points from 0 to 5. The total score can therefore range from 0 to 35 (asymptomatic to very symptomatic). It is widely used and reliable measure of lower urinary tract symptoms. It takes approximately 2 minutes to complete.

Data Collection & Management

Attendance Recording

Group leaders (clinicians) will be given an attendance record of the anticipated participants in their group and will be responsible for ensuring scheduling and other clinical matters are managed once the groups start. The attendance record will only include a participant’s name and MRN. This will be confirmed by a member of the research team. The clinician will record the subject’s absence or presence for each session on the record.

Revision Date: December 1, 2003

Vanderbilt University Medical Center

Study #: 170652

Revision Date: 2/10/2020

Completed attendance records will be uploaded and stored on a limited access folder on the secure VUMC network drive. Only [name] and members of the research team will have access to this drive. The hard copies of these attendance records will be destroyed once they are uploaded to the drive at the end of each treatment group.

Data Collected during Treatment Sessions

Participants will complete and hand in a form regarding their completion of tasks or “homework” assigned by the clinician from the previous session.

In addition, participants will complete and hand in forms before and after each session that include questions regarding pain intensity and comfort level, as well as questions about what the participants have found helpful or non-helpful about the treatment.

Finally, study clinicians will complete a form each session that captures information regarding the perceived engagement of each participant in that particular session. All of these forms will be labeled with a subject’s name.

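### The gap between the pre-treatment pain score and the first hypnosis session is not controlled, so any change in pain before session 1 counts as treatment effect

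*Combined protocol and SAP*

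**What the plan says.** **Timing of the pre score.** Under Timetable in Section 5.0, once a person is found eligible, "they will complete informed consent and an assessment battery online or via computer on-site at OCIM either the same day", or on a later visit if requested. Then: "They will then be enrolled in the next group series, which we anticipate to occur roughly every two months". The next sentence gives a slightly different frequency: "With groups occurring 5 times per year with 15 participants, we anticipate a study inclusion rate of 75" per cent.

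**Start of a group.** Under Treatment Phase: "Groups will be scheduled to start when at least ten participants are enrolled". The maximum is fifteen. Section 4.0 mentions a "long waiting list for hypnosis treatment".

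**Latest completion.** Under Pre-treatment Assessments, the team first contacts the person, among other things to confirm when the group meets. Those who wish to enrol are then emailed the consent form and the link to the battery. Anyone who has not finished online before the group begins may complete it in clinic.

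**Pain at session 1.** Under Data Collected during Treatment Sessions, "participants will complete and hand in forms before and after each session that include questions regarding pain intensity and comfort level". For research participants this information is kept and entered in RedCap.

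**Analysis.** Section 2.0 lists one pre-treatment assessment. Section 4.0 states that nobody is randomized. Section 8.0 tests the primary outcome by a repeated-measures ANOVA of pre against post, which with two occasions is a paired t-test. The text supplied sets no maximum gap between the battery and session 1 and does not adjust for the gap.

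**The concern.** Hypothesis 1 attributes the pre-to-post fall in pain to eight hypnosis sessions. If the pre score was taken some weeks before session 1, the measured change covers an untreated stretch as well as the treatment. With no second arm, nothing in the analysis separates the two. The stretch also differs between participants, because it depends on when each became eligible relative to the next series and on when each filled in the battery. The pre/post difference is the whole basis of the efficacy claim in Aim 1, and the plan intends to use these data to apply for a larger trial.

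**Working it through.** The plan gives no figure for the gap, the SD, the expected change or power, so there is no stated result to reproduce. The check has three parts.

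**1. How long the gap could be.**
- Inputs from the Timetable text: series every 2 months, or 5 per year (12/5 = 2.4 months apart).
- Assumptions: 52/12 weeks per month, eligibility dates spread evenly between series, and the battery completed at once on eligibility.
- Spacing: 2 × 52/12 = 8.7 weeks, or 2.4 × 52/12 = 10.4 weeks.
- Mean gap = half the spacing: 4.3 or 5.2 weeks. The maximum is 8.7 or 10.4 weeks, and longer if a series is full or has not reached ten.
- Session spacing is not stated. If sessions are weekly, the course lasts 7 to 8 weeks and the untreated share of the pre-to-post interval is gap/(gap + course). On average this runs from 4.3/(4.3 + 8) = 35% to 5.2/(5.2 + 7) = 43%. At the maximum it runs from 8.7/(8.7 + 8) = 52% to 10.4/(10.4 + 7) = 60%.

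These values describe immediate completion. People who complete the battery at group start have a gap of zero, and the documents do not say how the sample divides.

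**2. What a change before session 1 does to the primary test.**
- Input from Section 3.0: 60 completers.
- Assumptions: two-sided 5% level, SD of change 1.5 to 2.5 NRS points, no effect of hypnosis, and a given mean fall before session 1.
- Noncentrality = fall/(SD/√60). Example: 0.5/(2.0/√60) = 1.94. The critical t on 59 degrees of freedom is 2.001, which gives probability 0.48.

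| Mean fall before session 1 | SD 1.5 | SD 2.0 | SD 2.5 |
|---|---|---|---|
| 0.25 | 0.25 | 0.16 | 0.12 |
| 0.50 | 0.72 | 0.48 | 0.33 |
| 0.75 | 0.97 | 0.82 | 0.63 |

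The smallest significant mean change is 2.001 × SD/√60. At SD 2.0 this is 0.52 points.

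**3. Whether the waiting time can act as each person's own control.**
- Assume SD 2 on each occasion and correlation 0.7 between occasions.
- Simple change has SD 2√(2 × 0.3) = 1.55 and 95% CI half-width 2.001 × 1.55/√60 = 0.40.
- The contrast of treatment change minus waiting change has SD 2√(6 × 0.3) = 2.68 and half-width 0.69. It compares intervals of unequal length.
- Put per week, with a 7-week course and gap w, its variance is 2² × 0.3 × [2/49 + 2E(1/w²) + (2/7)E(1/w)]. For gaps uniform from 1 to 10.4 weeks, E(1/w²) = 0.096 and E(1/w) = 0.249. The SD is then 0.60 and the half-width 0.16 points per week, or 1.1 points over 7 weeks. Shorter gaps make it worse, and at zero gap it is undefined.

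A per-week within-person contrast is therefore not worth planning.

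**The case against.** The strongest reply is that the plan is better than the Timetable paragraph suggests. The battery link goes out after the group dates have been discussed, and completion is allowed up to group start, so many gaps may be short. A pain rating before session 1 is already collected and stored. Entry requires pain of at least three months' duration that is present at least 75% of the time, so nothing shows that pain would fall during a wait. Any single-arm pilot shares the problem of natural course.

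Much of this stands, and it rules out several stronger readings that a reader might infer:

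- *Most participants wait a month or more untreated.* Not established. The 4.3 to 5.2 week mean assumes that everyone completes the battery on becoming eligible. The waiting list in Section 4.0 is for hypnosis treatment, and nothing shows that people wait on it after completing the battery.
- *The waiting interval is lost because pain is not measured at its end.* Not so. A rating exists. What is missing is its recall period and any role for it in Section 8.0.
- *Other care starts at intake for everyone.* Section 4.0 says that patients "are seen by a provider first-hand in order to establish an integrative treatment plan as a part of their treatment". Establishing a plan is not the same as starting care, and the same section allows telephone screening when a provider cannot screen. Concurrent care during the gap is possible but not documented.
- *The BPI is certainly not repeated at session 1.* Table 1, which holds the schedule of measures, is not in the text supplied, and Section 2.0 has outcomes assessed three times during treatment without naming the sessions.

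None of this closes the gap. Optional late completion makes the interval variable without bounding it, and Section 8.0 as written would still count all change after the pre score as treatment change.

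**Conclusion.** The concern holds in a limited form. The interval from the pre score to session 1 is uncontrolled and can run from zero to about two months or more. With no comparator and a plain pre/post test, whatever happens to pain in that interval is attributed to hypnosis. The documents do not show how large the change would be or in which direction. The probability of 0.48 for a 0.5-point fall rests on an assumed SD of change of 2.0, 60 completers, a two-sided 5% test and no hypnosis effect; over SDs of 1.5 to 2.5 it ranges from 0.72 to 0.33. The remedy removes only the part of the bias that arises before session 1. It is worth making because it costs little and the primary claim depends wholly on the pre/post difference.

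**What to change.** 1. Have the research team, not the group clinicians, collect the four past-week BPI severity items within the few days before session 1, by RedCap link or on arrival. Section 5.0 limits clinicians to standard-care activities, so this should not simply be added to their session form.
2. State in Section 8.0 that this is the pre value for Hypothesis 1. Use the consent value for anyone who lacks it, and run a sensitivity analysis with the consent value for everyone.
3. As supportive description only, report the mean change with 95% CI from consent to session 1 beside the mean change from session 1 to post-treatment, with the distribution of waits. Do not plan a per-week within-person contrast.

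If Table 1 already places the BPI at session 1, only the wording in Section 8.0 is needed.

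**Cost:** about a minute of extra data collection per participant (Section 5.0 puts the four items at under one minute), a short addition to Section 8.0, a possibly smaller reported change, and a baseline whose source differs for a few participants. Change during the treatment weeks remains uncontrolled and should be stated as a limitation.

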7.0 Study Withdrawal/Discontinuation

Treatment Withdrawal

Participants may withdraw from the study at any time without loss of payment. Individuals may be withdrawn from the study if the PI learns that a participant does not meet study inclusion criteria after assessments have been completed. These participants will still be offered the clinical service. If this occurs, the data will not be recorded into the database and the participant will be withdrawn from the sample.

Treatment Intervention Discontinuation

As per standard clinical procedures, a participant will be withdrawn from the treatment intervention if s/he (1) engages in behavior that is disruptive to the group, and/or (2) engages in behavior that interferes with the appropriate administration of the group treatment.

However, participants who are withdrawn from the study treatment intervention will be invited to complete study assessments during treatment, post-treatment, 3-month and 6-month follow-up in order to allow for complete data for the planned intent-to-treat analyses. Participants will receive payment for the time it takes to provide outcome data at each assessment point.

8.0 Statistical Considerations

The hypotheses outlined above will be tested through bivariate correlation, t-tests, and repeated-measures regression analyses. Specifically, relationships among variables of interest (Hypotheses 1) will be assessed through Pearson product-moment correlation analyses to determine the strength of the association among these constructs in our sample and a repeated measures ANOVA to assess change in the primary outcome measure (NRS pain intensity) pre and post-treatment. Tests of moderation (Hypotheses 2) will be tested using multiple linear regression with cross-products of the variables of interest to assess the interaction between predictors. All analyses will be carried out on either SPSS 22 (IBM, 2013) or the R statistical package (57)

9.0 Privacy/Confidentiality Issues

Minimization of risk: As per standard clinical care, potential group participants will be screened by an OCIM medical or behavioral health provider prior to enrollment utilizing the hypnosis referral form. Participants in any acute emotional distress, with cognitive limitations, or considered to be unstable behaviorally or psychologically will not be referred to group.

Informed consent will be obtained electronically or on paper (if assessments completed in clinic) for each participant in the study prior to their participation. Assessment data will be entered and stored using RedCap/SPSS in encrypted files on an encrypted laptop computer belonging to the PI. Participant tracking information will be stored on a separate password-protected excel file only accessible to the PI and a research team member. Paper assessments will be entered into Redcap by a member of the research team and de-identified following completion. They will be given a unique number, with tracking information of this number only accessible to the PI and members of the research team. Consent forms completed on paper will be stored in a separate file in a locked cabinet. A limited data set, containing no identifying information, may be shared

Vanderbilt University Medical Center

Study #: 170652

Revision Date: 2/10/2020

with collaborating individuals at regional institutions. Such individuals will have signed Data Use Agreements with VUMC and will abide by these contracts prior to having access to any such information.

The proposed study design involves non-invasive procedures. The data described other than the data collected during the group treatment sessions will be collected solely for research purposes (e.g. assessments, medical record data, demographics). Participants will be informed that data collected before and after treatment sessions, i.e. data regarding homework practice, pain intensity and comfort before and after each treatment session, and participant engagement as per the study clinician, will be reported in their medical record, as clinically indicated. Research participation will not influence any part of a patient's medical treatment.

